	
scores, which may include a 11 point numerical pain score scale, or other patient-reported outcomes related to the pain etiology. Subjects will document outcomes as instructed by the site at the Enrollment Visit.
 
The site will contact the subject via telephone or the subject will come for an interim visit at regular intervals (to be determined by the investigator based on treatment regimen and standard of practice) to assess subject adherence to treatment, completion of patient reported outcomes, NPRS, CGI-I, PGIC and any safety concerns and/or changes in concomitant treatments/medications.
 
After up to 20 weeks of treatment, the subject will return to the clinic for a final assessment that will include the NPRS, CGI-I and PGIC. Adverse events and changes in concomitant medications will be collected.
 
Three months post-treatment, a follow-up phone call will be made to collect the NPRS.

Study Device	
The study device is the Provant[®] Therapy System which delivers Pulsed Electromagnetic Field (PEMF) energy therapy. Each device will be identified by a unique serial number.

Study Sample	
The anticipated enrollment in this study is up to 300 subjects. The study will be conducted at multiple (up to 25) sites.

Outcome Measures	
Outcome measures will be assessed in order to allow for characterization of the response to PEMF therapy.
 
Efficacy Assessments
 
Outcome measures of response to treatment with Provant will be determined based on the pain and/or edema being treated. The initial evaluations will include treatment of post-surgical hand edema, arterial insufficiency, diabetic peripheral neuropathy, abdominoplasty and other plastic surgeries, post-hernia surgical pain, and pelvic pain. All outcome measures used as part of the standard of practice regimen will be non-invasive assessments e.g., pain scores, SF-36, ankle-foot scales, oxygen perfusion (MOXY), and diaries with some subjects. Protocol required assessments will include the NPRS, CGI-I and PGIC.
 
Subject adherence (compliance with the prescribed treatment regimen) will be assessed verbally during follow-up and upon completion of the treatment period. A subject with complete adherence will be expected to have a usage meter reading of 1.0 for every hour that the subject treated.

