10. Subject has been previously treated with the Provant Therapy System.
11. Subject is unwilling or unable to follow study instructions, or comply with the treatment regimen and study visits.

E. Recruitment

Study subjects will be drawn from the investigative site.

F. Randomization

This is an open-label study. No subject randomization will occur. Each Provant Therapy System will have a unique serial number that will be recorded on the eCRFs.

G. Device Description

The Provant Therapy System is a solid-state, fixed-power output radio frequency generator and transmitter designed to operate at the Federal Communication Commission authorized medical device frequency of 27.12 MHz. The Provant System's primary components are the Control Unit, the Treatment Applicator that generates and delivers the shortwave RF energy, and single-use Disposable Applicator Covers intended to minimize contagion transmission and help protect the Treatment Applicator from biological contamination. Key functions and features of these components are as follows:

1. Control Unit

The Control Unit contains the main electronics, software, and user interface of the Provant System. The Control Panel has a Therapy Start/Stop Switch and two Therapy Status Indicators, described below, which are located on the top of the Control Panel, as well as a Usage Meter on the side of Control Panel.

Pressing the Therapy Start/Stop Switch initiates a preset, thirty (30)-minute therapy session by starting the Radio Frequency Identification Device (RFID) Tag interrogation and treatment sequence described in greater detail below. Pressing the Therapy Start/Stop Switch again after a therapy session has started will stop the RF energy generation. When pressed, the therapy Start/Stop switch generates an audible tone to inform the user that therapy is being initiated or terminated.

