5. Conduct baseline efficacy assessments.

Response to treatment with Provant will be determined based on the location of the subject's treatment area. Assessments will include the NPRS and non-invasive assessments part of the investigator's standard of practice e.g., pain scores, SF-36, ankle-foot scales, oxygen perfusion (MOXY), and diaries with some subjects.

6. If the subject continues to meet eligibility criteria, enroll subject, and dispense study device.
7. Introduce and train the subject on the use of the Provant Therapy System, including instructions for proper positioning and operation of the device.
8. If applicable, distribute a patient diary and instruct the subject on how to complete. Examples of diary collection tools are provided in Appendix B.

During this visit, eligible subjects will receive a Provant device and up to 120 Disposable Applicator Covers (packs of 30, depending on the anticipated treatment duration) and the subject will be instructed to administer treatment as prescribed by the investigator.

C. Treatment Period

Treatment may be self-administered by the subject, or with the assistance of a family member or caregiver. Subjects will assume a comfortable position and place the treatment applicator pad of the Provant device centering the applicator pad on the treatment location as instructed by the investigator. Treatment will be administered for 30 consecutive minutes.

Subjects will be asked to complete the patient reported outcome form(s) as instructed (as applicable).

D. Interim Visits

Subjects will be required to return to the clinic during the course of treatment as instructed by the investigator. Telephone follow-ups may also be performed with each subject as determined by the investigator. At these interim visits, the following will be collected if assessed:

1. Review and record adverse events
2. Review and record all concomitant medications
3. Assess adherence to Provant treatment regimen

4. Assess completion of the patient reported outcome form(s), as applicable
5. Conduct efficacy assessments:

Response to treatment with Provant will be determined based on the location of the subject's treatment area. Assessments will include the NPRS, CGI-I, PGIC and non-invasive assessments part of the Investigators standard of practice e.g., pain scores, SF-36, ankle-foot scales, oxygen perfusion (MOXY), and diaries with some subjects.

E. End of Treatment Visit

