Subjects will return to the clinic after completion of treatment as required by the study investigator. At this visit, the following procedures will be performed:

1. Collect subject's weight
2. Review and record adverse events
3. Review and record all concomitant medications
4. Conduct efficacy assessments:

Response to treatment with Provant will be determined based on the location of the subject's treatment area. Assessments will include the NPRS, CGI-I, PGIC and non-invasive assessments part of the Investigators standard of practice e.g., pain scores, SF-36, ankle-foot scales, oxygen perfusion (MOXY), and diaries with some subjects.

5. Return of study device and unused DACs
6. Return of the patient reported outcome form(s), as applicable. Examples of diary collection tools are provided in Appendix B.

F. Post-treatment Phone Call

Three months after the End of Treatment Visit, subjects will be contacted via telephone and asked to rate their pain using the NPRS.

G. Treatment adherence/study compliance

Subject adherence (compliance with the prescribed treatment regimen) will be assessed during interim visits and upon completion of the treatment period by the research staff reading and recording the number displayed on the study device usage meter. The usage meter will read 0.0 when dispensed. A subject with complete adherence will be expected to have a usage meter reading of 1.0 for each hour of treatment.

Subjects will be instructed to return any unused DACs at the End of Treatment visit. Compliance will be assessed by counting the number of returned, unused DACs, and subtracting this from the total number of DACs dispensed (120). As each treatment session requires one new DAC, compliance can be calculated based on the number of returned DACs relative to the prescribed regimen.

H. Protocol Adherence

If protocol modifications are necessary, all alterations that are not solely of an administrative nature require a formal protocol amendment.

If an investigator has deviated from the protocol in order to eliminate an immediate hazard to subjects or for other inevitable medical reasons, the investigator shall document all such deviations, including the reasons thereof, and immediately submit the documentation to the sponsor and to the IRB if required.

I. Concomitant Medications

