All concomitant drug and non-drug treatments as well as the frequency of administration and indication for the treatment will be recorded in the subject's chart. Based on the subject's pain etiology, the investigator may disallow certain concomitant medications in order to accurately assess the effect of Provant therapy. Opioid or other pain drug therapies may be reduced or discontinued during the treatment period of the study as directed by the subject's treating physician.

It is important to record the reason why each analgesic medication is being taken by the subject, specifically analgesics taken for treatment of pain/edema. In this context, "analgesic medications" refers to medications prescribed and administered for the treatment of pain, and includes but is not limited to opioids, nonsteroidal anti-inflammatory agents, anti-depressants and muscle relaxants.

Prohibited Medications/Treatments

The following medications and therapeutics are prohibited throughout the study:

- Systemic steroids or topical steroids on the treatment location
- Transcutaneous electrical neurostimulators (TENS units)
- Implanted neurostimulators
- Local injections
- Intrathecal infusion
- Acupuncture
- Surgery

V. WITHDRAWAL PROCEDURES

If a subject or the prescriber decides to discontinue the subject's treatment with the device, efforts will be made to perform all assessments scheduled for the End of Treatment Visit prior to subject withdrawal.

VI. STATISTICAL CONSIDERATIONS

The statistical analysis of the study is described in detail in a separate version-controlled Statistical Analysis Plan (SAP). However, the statistical methodology described in this section of the protocol will be the basis for the detailed SAP.

Where not otherwise specified, the last pre-treatment observation will be used as baseline for calculating post-treatment changes from baseline. All confidence intervals will use a significance level of 5%.

A. Study Populations

Safety summaries will be conducted on all subjects who undergo treatment.

The effectiveness summaries will also be conducted on all subjects who undergo treatment. Subjects that do not attend the End of Treatment Visit will be excluded from the End of Treatment analyses. Subjects who complete the End of Treatment Visit will be assessed for efficacy regardless of the number of days of treatment received. No imputation of data will occur.

B. Efficacy Data Summaries

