#### **Assessment of Compliance and DC packs**

##### **Compliance (Yes or No)**

##### **Total number of pack provided**

##### **Provant Device Return (End of Treatment Visit)**

Edema Evaluation at treatment site

- Mild, Moderate, Severe
- Pitting: Non-pitting, 1+, 2+, 3+, 4+, Lymphedema

Weight (End of Treatment Visit)

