### 10.1. Treatment Administration and Accountability

A summary of Provant treatment regimen will be presented in Table 14.2.1 entitled *Summary of the Provant Treatment Regimen (ITT / Safety Population)*. The frequency of treatment and length of the individual treatment sessions will be summarized using counts and percentages. Listing 16.2.8 entitled *Study Device – Application and Accountability* will contain all of the recorded treatment information; this listing will be sorted by subject number.

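### Protocol IV.G fixes covers dispensed at 120, the maximum under IV.B, so the cover count overstates sessions for anyone given fewer

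*Protocol*

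**What the plan says.** Protocol IV.B (Enrollment Visit) has each eligible subject leave with a device and "up to 120 Disposable Applicator Covers (packs of 30, depending on the anticipated treatment duration". The supply is therefore meant to differ between subjects, and 120 (four packs) is the most anyone receives at that visit.

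Protocol IV.G (Treatment adherence/study compliance) gives two adherence measures. One is the device's usage meter. The other is a cover count: staff count the unused covers returned at the End of Treatment Visit, "subtracting this from the total number of DACs dispensed (120". It then adds: "As each treatment session requires one new DAC, compliance can be calculated based on the number of returned DACs relative to the prescribed regimen".

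SAP 3.2.2 lists a Yes/No compliance item and "Total number of pack provided", but gives no formula linking the two. SAP 10.1 says that Listing 16.2.8 "will contain all of the recorded treatment information"; it gives no derivation of sessions used.

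**The concern.** IV.G puts a single number where IV.B says the number varies. The two sections agree only for subjects given exactly four packs. For everyone else the printed subtraction treats covers that were never handed out as covers used.

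Treatment is self-administered at home, so the meter and the cover count are the only objective checks on it that IV.G offers. If staff use 120, the cover count, and any Yes/No compliance item based on it, is too favourable for subjects given fewer covers. It would also disagree with the meter for no real reason. With up to 25 sites, some may use the printed figure and others the actual supply. Recording real-world use is the SAP's stated intent (SAP 4.3), so sessions used is worth getting right even in a descriptive study.

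**Working it through.** **Inputs**

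- Covers dispensed, D: whole packs of 30 up to 120 (Protocol IV.B), so D = 30, 60, 90 or 120. Whole packs and no resupply are assumptions.
- Unused covers returned, R: counted per subject (Protocol IV.G).
- Covers per session: 1 (Protocol IV.G).
- Printed constant: 120 (Protocol IV.G).

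**The plan's figure.** 4 packs × 30 = 120. It matches IV.B only as the maximum.

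**Error of the rule.** Covers used are U = D − R. The rule as printed gives 120 − R = 120 − (D − U) = U + (120 − D). The overcount is 120 − D and does not depend on R.

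| D | Overcount (120 − D) | Credited if all used (R = 0) | True | Credited if none used (R = D) | True |
|---|---|---|---|---|---|
| 30 | 90 | 120 | 30 | 90 | 0 |
| 60 | 60 | 120 | 60 | 60 | 0 |
| 90 | 30 | 120 | 90 | 30 | 0 |
| 120 | 0 | 120 | 120 | 0 | 0 |

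**As a compliance percentage.** Assume the prescribed number of sessions equals D and half are used, so true compliance is 50%. The printed rule gives (120 − D/2)/D:

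- D = 30: 105/30 = 350%
- D = 60: 90/60 = 150%
- D = 90: 75/90 = 83%
- D = 120: 60/120 = 50%

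**Would the error show itself?** The documents describe no check for more covers used than dispensed. If one were run, it would flag a subject when U + (120 − D) > D, that is, when U > 2D − 120.

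- D = 30: the threshold is −60, so every subject is flagged.
- D = 60: the threshold is 0, so every subject who used at least one cover is flagged.
- D = 90: the threshold is 60. Subjects who used 0 to 60 covers are credited with 30 to 90 sessions and pass unnoticed.

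**Against the meter.** Pressing the start switch "initiates a preset, thirty (30)-minute therapy session" (Protocol III.G.1). If every used cover stands for a full 30-minute session, the cover count exceeds the meter by 90 × 0.5 = 45, 60 × 0.5 = 30 or 30 × 0.5 = 15 hours. These gaps hold only under that condition. SAP 3.2.1 also lists 15-minute and other session lengths. With D = 30 and all covers used at 15 minutes, the gap is 120 × 0.5 − 30 × 0.25 = 52.5 hours.

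**The opposite direction.** Treatment may last 20 weeks, and once-daily use for that long is 20 × 7 = 140 sessions, more than 120 covers allow. No resupply is described. If it happened, the same constant would understate use: with five packs, 120 − 150 = −30 sessions.

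**The case against.** The best reply is that the governing words in IV.G are the total dispensed, with 120 only a parenthesis showing a full supply. Staff who take the words and ignore the number get the right answer, and the following sentence ties compliance to the individual regimen. SAP 3.2.2 also places packs provided next to the compliance item, so the right input is planned data and blind use of 120 is less likely. This is fair, and it means we cannot say how many sites would make the error. It does not remove the problem: 120 is the only value the rule prints, the text supports two different results, and no formula in the SAP text we have says which to use.

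It can also be said that little depends on the count. That stands. The meter does not depend on covers. Subjects who complete the End of Treatment Visit "will be assessed for efficacy regardless of the number of days of treatment received" (Protocol VI.A). No formal hypothesis test is planned, and the treatment and efficacy tables described in SAP 10.1 to 10.3 do not summarise compliance.

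**Conclusion.** The point holds and is minor. Protocol IV.B and IV.G conflict: one gives 120 as a maximum, the other as the number dispensed. Applied with the printed figure, the rule overstates sessions by exactly 120 − D: 90, 60 or 30 for one, two or three packs, assuming whole packs and no resupply. The result is wrong for every such subject regardless of how many covers come back, and for some subjects given 90 covers it looks plausible.

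The study-wide effect cannot be computed, because the documents do not say how many subjects receive fewer than four packs. Only the description of adherence is affected, not any planned efficacy or safety result.

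**What to change.** In Protocol IV.G, replace the parenthetical 120 with the number of covers actually dispensed to that subject: 30 × total packs provided, counting the Enrollment Visit packs and any later supply. This also removes the undercount if covers are ever resupplied. In the next sentence, compare covers used (dispensed minus returned) with the covers the prescribed regimen requires, rather than relating the returned count directly to the regimen.

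The cost is two protocol sentences and a one-line derivation. SAP 3.2.2 already lists packs provided. The sponsor should confirm that this item includes the packs given at enrollment and that the number of returned covers is captured in the data.

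Optionally, while the section is open, clarify the meter standard. The Synopsis says: "A subject with complete adherence will be expected to have a usage meter reading of 1.0 for every hour that the subject treated". Read literally, that compares the meter with hours treated, not hours prescribed. IV.G has similar wording, so both places would need the edit.

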Thirty subjects in this study were evaluated for the effectiveness of the Provant Therapy System in the treatment of post-surgical pain after back surgery. Provant treatment twice daily for 45 days was associated with improved pain scores, improved overall well-being, improved physical function, and reduced analgesic consumption, especially in subjects who had undergone a discectomy.

The purpose of the current study is to confirm the findings of pain relief observed in patients receiving treatment with Provant in a “real-world”, post-market setting. Data from this study may be combined with other studies conducted in the post-market setting, i.e., in a patient registry.

II. STUDY OBJECTIVES

This study is designed to provide post-market evidence of the safety and effectiveness of the Provant Therapy System for improving pain and edema in subjects with multiple pain etiologies.

III. STUDY DESIGN

A. Study Design

The study is an open-label, non-controlled study of the safety and effectiveness of investigator determined Provant therapy in subjects with pain and/or edema from various pain etiologies.

B. Efficacy Assessments

Outcome measures of response to treatment with Provant will be determined based on the location of the subject's treatment area. Protocol required assessments will include baseline and interim / end of treatment visit and 3-month follow-up (post-treatment) pain scores using an 11-point numeric pain rating scale (NPRS), and a Clinical Global Impression – Global Improvement (CGI-I) Scale and a Patient Global Impression of Change (PGIC) Scale. All outcome measures used in the investigator's standard of practice are non-invasive assessments, e.g., pain scores, SF-36, ankle-foot scales, oxygen perfusion (MOXY), and diaries with some subjects.

C. Safety Evaluation

All observed and reported adverse effects will be recorded by the research staff. Start dates, end dates, frequency, severity of the event, any treatment required to treat the event, and the investigator's judgment on causality and relationship to the device will be assessed for each AE. Any AE occurring after the signing of the informed consent form will be recorded. Only those AEs occurring after initiation of the first treatment with the study device will be considered treatment-emergent AEs.

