The two Therapy Status Indicators on the Control Panel indicate when therapy is underway and the amount of time (in minutes) remaining in the therapy session. When treatment is initiated, the message "CPI RUNNING" is displayed and green bars scroll from left to right across the indicator window. When the thirty-minute therapy session is concluded, the generation of RF energy is automatically terminated, the Therapy Status Indicator windows go blank, and a brief audible beep is generated to alert the user that the treatment is finished. The user will then be instructed to turn off the Power Switch, remove the used Disposable Applicator Cover, and store the Treatment Applicator and cable until the next use.

2. Disposable Applicator Covers.

The Provant Therapy System features Disposable Applicator Covers, which are placed over the Treatment Applicator (described below) before each therapy session. The Disposable Applicator Covers of the Provant Therapy System are single-use-only and are intended to minimize contagion transmission and help protect the Treatment Applicator from biological contamination. Embedded in the Disposable Applicator

Covers is RFID reader functionality that is controlled by software in the Provant Control Unit. This software prevents the reuse of a Disposable Applicator Cover by confirming that a new Disposable Applicator Cover is in place before allowing the generation and delivery of the therapeutic RF energy. If the user attempts to reuse a cover, the device recognizes the RFID tag on the cover at start up as “used” and will generate an audible alert to inform the user to replace the used cover with a new cover. If the user attempts to use the device without a Disposable Applicator Cover in place over the Treatment Applicator, the device will generate an audible alert to remind the user to place a new cover. In either scenario, the Provant Therapy System will not initiate a therapy session until a new Disposable Applicator Cover is in place. The used Disposable Applicator Covers will be discarded as standard (not bio-hazard) waste.

3. Treatment Applicator Pad

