### **Provant Treatment Regimen**

Frequency of Treatment:

- Q.D. (every day)
- B.I.D (twice daily)
- PRN (as needed)
- Other (specific information will be included in a listing)

Length of individual Treatment Session:

- 30 minutes (default)
- 15 minutes
- 1 hour (two 30 minute sessions)
- Other (specific information will be included in a listing)

Weight

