## 6. ANALYSIS POPULATIONS

The results from this study will be presented using a single population.

- **ITT / Safety Population:** All subjects who are consented and treatment with the study device is initiated, independent of the treatment being successful implemented.

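### Protocol IV.G counts covers used by subtracting returns from a fixed 120, although IV.B dispenses packs of 30 with 120 only as the maximum

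*Protocol*

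**What the plan says.** Protocol IV.G (Treatment adherence/study compliance) gives two adherence measures. The first is the device usage meter, read at interim visits and at the end of treatment, which should advance 1.0 per hour of treatment. The second is a cover count: staff count the unused covers returned, "subtracting this from the total number of DACs dispensed (120"), and relate the result to the prescribed regimen. The stated basis is "As each treatment session requires one new DAC", and the device enforces this, because "the Provant Therapy System will not initiate a therapy session until a new Disposable Applicator Cover is in place" (Protocol III.G.2).

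Protocol IV.B (Enrollment Visit) sets what is dispensed: "up to 120 Disposable Applicator Covers (packs of 30, depending on the anticipated treatment duration").

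The Synopsis (Outcome Measures) adds that adherence "will be assessed verbally during follow-up and upon completion of the treatment period".

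SAP 3.2.2 lists compliance as a yes/no item and, next to it, the number of packs provided. It gives no formula or threshold for deriving the yes/no answer.

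**The concern.** IV.B makes 120 a ceiling that depends on how long treatment is expected to last. IV.G treats the same number as what every subject received. The two agree only for a four-pack subject. For anyone given fewer packs, the difference between 120 and the true number dispensed is counted as covers used, although those covers never left the clinic.

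For these subjects the error always makes adherence look better than it was. With three packs it can also produce a believable figure, so a subject who skipped a third of the sessions can look fully compliant. At stake is the accuracy of the cover-count check, and of any yes/no compliance entry that a site bases on it.

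**Working it through.** **Inputs.** Pack size 30 and maximum 120 (Protocol IV.B); fixed starting figure 120 and one cover per session (IV.G); 30-minute preset session (III.G.1). Assumptions for the illustration: sessions prescribed equal covers dispensed, and every unused cover comes back, as IV.G instructs.

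**The plan's own figure.** 4 packs × 30 = 120. The figure is reproduced, but only for four packs.

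**Formulas.** Let D be covers dispensed, R covers returned, U covers used and P sessions prescribed. With full return, R = D − U.

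- Rule as written: covers used = 120 − R = U + (120 − D).
- Correct: covers used = D − R = U.
- Overcount = 120 − D covers. As a share of the prescription the error is 100 × (120 − D)/P percentage points.

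IV.G says only that compliance can be worked out relative to the prescribed regimen. Dividing by P is the natural reading, but no explicit percentage formula is printed.

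| Packs | D | Overcount (covers) | Error if P = D (points) | Fully adherent subject computes as |
|---|---|---|---|---|
| 4 | 120 | 0 | 0 | 120/120 = 100% |
| 3 | 90 | 30 | +33.3 | 120/90 = 133.3% |
| 2 | 60 | 60 | +100 | 120/60 = 200% |
| 1 | 30 | 90 | +300 | 120/30 = 400% |

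**Three packs, 90 sessions prescribed, 60 completed.** Returned: 90 − 60 = 30.

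- As written: (120 − 30)/90 = 100%.
- Correct: (90 − 30)/90 = 66.7%.
- Usage meter: 60 × 0.5 h = 30.0 h, against 90 × 0.5 h = 45.0 h expected, or 66.7%.

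**Where the computed value looks plausible.** For D = P = 90 the rule gives (U + 30)/90, which stays at or below 100% when U ≤ 60. One session computes as 31/90 = 34.4% (true 1.1%); 45 sessions as 75/90 = 83.3% (true 50%); 60 as 100%; 61 as 91/90 = 101.1%.

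**One and two packs.** With P = D, a single session already computes as 61/60 = 101.7% (two packs) or 91/30 = 303.3% (one pack), so the figure exposes itself. This depends on P. If two packs were set against 90 prescribed sessions, 30 completed sessions would compute as (60 + 30)/90 = 100%, against a true 33.3%.

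**Later packs.** The documents do not describe resupply, but once-daily treatment for the 20-week maximum is 20 × 7 = 140 sessions, more than 120 covers. If such a subject received five packs in all (150), used 140 and returned 10, the rule would give (120 − 10)/140 = 78.6% for a fully adherent subject. Here the fixed figure errs downward.

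**The case against.** The strongest reply is that the operative words of IV.G are sound: returns are subtracted from what was dispensed, and only the number in parentheses is wrong. The site knows how many packs it handed out, and SAP 3.2.2 lists that number. Staff would have to credit a subject with covers they know were never given. This stands as far as it goes: a site that ignores the 120 gets the right answer. It does not make the printed figure correct, and nothing in the SAP overrides it.

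The second reply is that the usage meter gives a cross-check. It does: 30.0 h against 45.0 h in the illustration. A reader might infer that the error would go undetected; the documents do not support that, because the meter is recorded for the same subject. They also do not say which measure prevails when the two disagree.

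The third reply is that nothing downstream depends on the figure, and this stands in full. A reader might infer that the study's adherence results or effectiveness summaries would be biased. The single analysis population is "All subjects who are consented and treatment with the study device is initiated" (SAP 6), with no adherence condition. Protocol VI.A assesses subjects who attend the End of Treatment Visit whatever number of days they were treated. SAP Table 14.2.1 summarizes only treatment frequency and session length.

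Two further inferences should be resisted. Ninety sessions also equals the twice-daily, 45-day schedule in Protocol Section I ("Provant treatment twice daily for 45 days was associated with improved pain scores"), but that was the earlier failed-back-surgery pilot. Here the investigator sets the regimen, so 90 is an illustration. Nor does every one- or two-pack subject necessarily compute above 100%; that is assured only when sessions prescribed do not exceed covers dispensed.

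**Conclusion.** The point holds and is minor: IV.G is wrong as written. Its fixed 120 conflicts with IV.B and overcounts use by 30, 60 or 90 covers for subjects given three, two or one packs. In the three-pack illustration this turns 66.7% into 100%. The cover overcount follows directly from the two sections; the percentages also rest on the assumed 90-session prescription, one cover per session and complete return of unused covers.

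The consequence stops at the cover-count check. No estimate, confidence interval or safety summary changes. How often the error would occur cannot be judged, because neither the number of subjects given fewer than four packs nor the sites' handling of the 120 is stated.

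**What to change.** In Protocol IV.G, replace the parenthetical 120 so that returns are subtracted from the covers dispensed *to that subject (30 × packs provided, including any later packs)*. In the illustration this gives (90 − 30)/90 = 66.7%, in line with the meter.

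The cost is one phrase. Packs provided is already an item in SAP 3.2.2, and visits, dispensing, tables and populations are untouched. IV.H requires a formal amendment for changes that are not solely administrative. This correction is arguably administrative; if the sponsor thinks otherwise, it can go with the next amendment.

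No further compliance rules are needed for this point. SAP 3.2.1 also allows as-needed use, 15-minute sessions and "1 hour (two 30 minute sessions"), but special wording for those regimens would not correct the 120.
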